6.12.7.1. Electrocardiograms

Electrocardiograms (ECGs) will be performed during screening (baseline), Cycle 2, 3, 4, and every other cycle (Cycle 6, Cycle 8, etc).

ECG assessment of normality and clinical significance will be listed by treatment group. Myocardial information and quantitative results including PR, QRS, QTc (corrected by concurrent RR), QTcB (Bazett’s correction), QTcF (Fridericia’s correction) and RR intervals will be provided in patient listings.

Changes in ECG parameters from baseline will be calculated and summarized at each visit.

6.12.7.2. Echocardiographs with Doppler

Echocardiography (ECHO) with Doppler will be assessed at screening, Cycle 2, 3, 4, and every other cycle (Cycle 6, Cycle 8, etc), Visit 801 and long term follow up as described above.

Echocardiography measurement values and changes from baseline will be listed for the following quantitative data: LV internal dimension, LA volume, LA dimension, LV ejection fraction, LV mass, PA systolic pressure, pulmonary flow velocity acceleration time, mitral deceleration time, mitral E/A ratio, and E/Em. Results will be listed by treatment, patient, cycle/visit, and parameter.

Echocardiography assessments with valvular regurgitation (aortic, pulmonary, mitral, and tricuspid regurgitation) will be listed by treatment, patient, cycle/visit, and study day.

Additionally, the frequency of maximum shift from baseline will be summarized by parameter and treatment.

RA dilation, RV dilation, left ventricular wall motion, and pericardial effusion will be listed by treatment, patient, cycle/visit, and study day. Additionally, the frequency of maximum shift from baseline will be summarized by parameter and treatment.

Graphical representation of LVEF may be provided if necessary.

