**Statistical Methods:**

Statistical: Approximately 120 patients will be randomly allocated to treatment in a 1:2:1 ratio (LY2157299 monotherapy/LY2157299 plus sorafenib therapy/sorafenib plus placebo therapy). This will provide about 83% power (strong prior) to detect a significant treatment difference in terms of OS between the LY2157299 plus sorafenib and sorafenib plus placebo using a Bayesian-augmented control design with a 1-sided alpha of 0.14 under the assumption that the true HR is 0.667 in favor of the LY2157299 plus sorafenib arm.

Efficacy: The primary analysis is to compare the OS between LY2157299 plus sorafenib with sorafenib plus placebo using a Bayesian OS model that augments current control data with additional information from historical data. The same Bayesian OS model will be used to estimate the HR between LY2157299 monotherapy and sorafenib plus placebo. HRs between the 3 treatment arms will also be estimated for TTP and PFS using proportional hazards models. ORR based on the RECIST v1.1 and mRECIST criteria will be calculated.

Safety: Summary statistics, plots, and listings for all safety data collected will be provided by arm.

Health Outcomes: Summary descriptive statistics by study part will be provided for the PRO data (ie, EORTC QLQ-30 and QLQ HCC-18) at each time point and change from baseline. Time to symptomatic progression will also be evaluated.

Pharmacokinetics: A population PK analysis will be performed on all patients receiving LY2157299. A PK analysis will be performed for sorafenib as well. This analysis will explore the impact of covariates such as demographic factors and markers on the relevant PK parameters.

Pharmacodynamics: Changes in response biomarkers, such as phosphorylated SMAD in tumor tissue (or other TGF- $\beta$ -related biomarkers), AFP L3, and E-cadherin in serum will be estimated and may be correlated with clinical efficacy. Exploratory population PK/pharmacodynamic analyses may be conducted to identify the exposure-biomarker response relationship.

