### **5.1.4. Nonclinical Toxicology of LY2157299**

The toxicity of LY2157299 has been characterized in repeat- and intermittent-dose, nonclinical safety studies up to 6 months duration in the rat and dog. The following paragraphs summarize the major findings in rats and dogs.

The heart and great vessels are major target organs for toxicity in both F344 rats and beagle dogs following treatment with LY2157299. These effects include valvulopathy and vascular lesions of multiple blood vessels at the base of the heart in rat and dog, which in the rat appear to be

partially reversible. In the rat, a continuum of changes in the gastrointestinal (GI) tract have been described, including inflammation of the mucosa, simple mucosal hyperplasia, and adenocarcinoma following 6 months of continuous treatment. Based on safety pharmacology studies, administration of LY2157299 produced increases in hexobarbital-induced sleep time. Administration of LY2157299 may produce dose-dependent hemodynamic side effects, measured by decreased blood pressure and increases in heart rate, which can be easily monitored in the clinic and are reversible upon cessation of treatment. The nonclinical data do not reveal any substantive clinical risk of QT/corrected QT prolongation at doses that result in total plasma concentrations of at least 3.3 µg/mL.

LY2157299 was negative in a bacterial mutation test (Ames test) and an in vivo mammalian test (mouse micronucleus). However, LY2157299 was positive in an in vitro mammalian test (chromosome aberration) with and without S9 activation. This positive finding is considered acceptable in the intended patient population.

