**Figure JBAS.8.2. JBAS extension period design.**

## 8.2. Discussion of Design and Control

Approximately 150 patients will be entered in order to randomly assign 120 patients to 1 of 3 treatment arms using a 1:2:1 allocation ratio in favor of the LY2157299 plus sorafenib arm. A randomized, controlled design is being used in this study. Randomization minimizes systematic

bias in the selection and assignment of patients to study therapy and provides justification for inferential statistical methods to be used on data from this study. The study will use a dynamic allocation method, introduced by Pocock and Simon (1975) (and extended for unequal treatment group sizes by Han et al. [2009]) to minimize imbalance between treatment arms according to factors such as AFP and portal vein thrombosis. Using an appropriate concurrent control arm (which is sorafenib in combination with placebo) enables direct statistical estimation of benefits and harms due to study therapy and minimizes bias in the assessment and interpretation of observed treatment effects. The rationale behind favoring the combination arm in the randomization is that this is the primary treatment of interest to compare with sorafenib alone. However, based on the longer time to progression observed in Study JBAK patients in whom LY2157299 was administered as a monotherapy in a first-line setting, there is medical need of getting more information for efficacy and safety of LY2157299 monotherapy. Therefore, a monotherapy arm is also included and will inform future Phase 3 development. The purpose of the monotherapy arm is to provide a comparison to assess the safety of LY2157299 compared to sorafenib. This is especially important because LY2157299 has shown preclinical cardiac toxicity, which, thus far, has not confirmed in clinical studies. However, sorafenib has known cardiac toxicity in patients. The 3-arm study will provide a better differentiation between the various safety profiles and inform the design of Phase 3. Since OS is not affected by pseudoprogression evaluations, OS is a preferred primary endpoint over TTP or PFS. A Bayesian design can be used to leverage survival data for sorafenib alone from historical clinical trials to benefit from the 2:1 randomization of the combination arm relative to sorafenib alone with the goal of increasing power over an otherwise similar design.

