### **12.2.11. Safety Analyses**

All safety summaries and analyses will be based upon the Safety Population as defined in Section [12.2.1](#).

Overall exposure to study drug, the numbers of patients completing each cycle, and the dose intensity will be summarized using descriptive statistics. The number of patients with any dose adjustment will be presented for entire treatment period as well as for each cycle. The number of patients with dose reductions, dose delays, or dose omissions will also be summarized, as will the reasons for dose adjustments.

An overall summary of AEs will be provided for AEs deemed by the investigator to be possibly related to study medication and will be repeated for events regardless of study drug causality. Incidence rates of these events will be compared between treatment arms using Fisher's exact test.

Safety analyses will include, but are not limited to, the following:

- all reported AEs, including seriousness, severity, and possible relationship to study drug, using CTCAE terminology and grades
- TEAEs, including seriousness, severity, and possible relationship to study drug, using CTCAE terminology and grades
- dose adjustments for any study therapy
- physical examination and other safety observations, including those specifically targeting the monitoring of cardiac safety
- laboratory measures

AE terms and severity grades will be assigned by the investigator using CTCAE version 4.0. MedDRA version 16 (or higher) will be used when reporting AEs by MedDRA terms. The MedDRA lower level term will be used in the treatment-emergent computation. A TEAE, defined as an event that first occurred or worsened in severity after baseline, will be summarized by SOC and by decreasing frequency of preferred term within SOC.

Laboratory and nonlaboratory CTCAEs will be summarized by CTCAE term and maximum CTCAE grade, including the total for maximum Grades 3 and 4. These summaries will be provided for events regardless of study drug causality and will be repeated for events deemed by the investigator to be possibly related to study medication.

Reasons for death will be summarized separately for on-therapy and within 30 days of last dose of study drug. SAEs will be summarized by preferred term.

Hospitalizations and transfusions during the study treatment period or during the 30-day safety follow-up period will be summarized by treatment group.

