6.12.6. Vital Signs and Other Physical Findings

Vital signs will be listed by patient, cycle and cycle day (baseline, Day 1 of each cycle, Day 14 of Cycles 1 and 2 only, and Visit 801). This listing will include height (at baseline), weight, heart rate, blood pressure, and ECOG performance status.

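### The SAP plans only patient listings for quantitative echocardiography (including LVEF), blood pressure and heart rate, where the protocol promises by-arm summaries

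*SAP*

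**What the plan says.** **Protocol.** The synopsis, under Statistical Methods, says of safety: "Summary statistics, plots, and listings for all safety data collected will be provided by arm". Section 12.2.11 includes among the safety analyses "physical examination and other safety observations, including those specifically targeting the monitoring of cardiac safety". Section 8.2 explains the third arm: "The purpose of the monotherapy arm is to provide a comparison to assess the safety of LY2157299 compared to sorafenib". It adds that this matters especially because LY2157299 showed preclinical cardiac toxicity and sorafenib has known cardiac toxicity. The same section also gives a wider reason: "there is medical need of getting more information for efficacy and safety of LY2157299 monotherapy". Section 5.1.4 warns of possible dose-dependent haemodynamic effects, namely "decreased blood pressure and increases in heart rate", reversible when treatment stops.

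**SAP.** Section 6.12.7.2 says: "Echocardiography measurement values and changes from baseline will be listed for the following quantitative data". Ten measures follow: LV internal dimension, LA volume, LA dimension, LV ejection fraction, LV mass, PA systolic pressure, pulmonary flow acceleration time, mitral deceleration time, E/A ratio and E/Em. On plots it says only: "Graphical representation of LVEF may be provided if necessary". Section 6.12.6 says: "Vital signs will be listed by patient, cycle and cycle day". That listing holds blood pressure and heart rate, including Day 14 of Cycles 1 and 2.

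**The concern.** A listing shows each patient's values but gives no mean, no spread and no count by arm. A modest average fall in LVEF, or a shift in blood pressure, could be present in one arm and go unseen by anyone paging through individual rows. These data are collected partly so that LY2157299 can be compared with sorafenib for safety. Attachment 14 of the protocol says that repeat echocardiograms serve to establish cardiac safety, and makes quantitative echocardiography the aim. If the SAP is followed as written, the report could meet the plan and still contain no by-arm result for ventricular function or blood pressure.

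**Working it through.** The plan states no figure on this point, so there is nothing to reproduce. The main check is textual.

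**1. What the SAP specifies, item by item**

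| Data | SAP section | Listed | Summarised |
|---|---|---|---|
| Ten quantitative echo measures, including LVEF | 6.12.7.2 | Yes | No (LVEF graph optional) |
| Valvular regurgitation (four valves) | 6.12.7.2 | Yes | Yes, maximum shift by treatment |
| RA/RV dilation, LV wall motion, pericardial effusion | 6.12.7.2 | Yes | Yes, maximum shift by treatment |
| ECG intervals, including RR | 6.12.7.1 | Yes | Yes, change at each visit |
| Cardiac-disorder adverse events | 6.12.7, 6.12.2 | Yes | Yes, by treatment group |
| Blood pressure, heart rate | 6.12.6 | Yes | No |

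Section 6.12.7.2 itself separates listing from summarising: the categorical items get both and the quantitative items only the first. Among these data, the gap is therefore quantitative echo, blood pressure and on-treatment heart rate.

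**2. Do the other summaries fill the gap?**

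- *Heart rate through RR.* Scheduled on-treatment ECGs fall on Day 1, predose, after the 14-day pause. Protocol 5.1.3 says LY2157299 is fully eliminated by then. The RR summary thus describes the off-LY2157299 state. The Day 14 vital signs are the scheduled readings within the dosing period, and they are only listed.
- *Cardiac adverse events.* Attachment 18 gives congestive heart failure in 1.9% of sorafenib patients. Used as an illustration, 30 patients give 30 × 0.019 = 0.57 expected cases, and the chance of seeing any is 1 − 0.981^30 = 44%. For 60 patients the figures are 1.14 and 68%. Event tables alone are a weak comparison.
- *Valve shifts.* These address valvulopathy, not ventricular function.

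**3. What a by-arm LVEF summary could show**

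Half-width of a 95% interval = t × SD × √(1/n1 + 1/n2). The arm sizes 30/60/30 come from SAP 5.2. The SD of LVEF change is not in the documents; 6 to 8 points is assumed, with 5 to 10 as the wider range.

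- Arm 1 versus Arm 3 (30 v 30, t = 2.002, root = 0.2582): SD 6 gives ±3.1 and SD 8 gives ±4.1. SD 5 and SD 10 give ±2.6 and ±5.2.
- Arm 2 versus Arm 3 (60 v 30, t = 1.987, root = 0.2236): SD 6 gives ±2.7 and SD 8 gives ±3.6.

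These figures require every patient to have paired data. If, as a further assumption, only half of Arms 1 and 3 did (15 v 15, t = 2.048, root = 0.3651), SD 6 gives 2.048 × 6 × 0.3651 = ±4.5 and SD 8 gives ±6.0.

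**The case against.** **The main cardiac signal is already summarised.** The nonclinical heart findings are valvulopathy and vascular lesions, not a fall in LVEF, and the echo-based discontinuation rule in Protocol 9.4.1.1 concerns heart valves. Valvular regurgitation does get a by-treatment summary. This stands. A reader might infer that the cardiac comparison receives no estimate at all; the table above shows that it does not go that far.

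**The monotherapy arm has other reasons.** Protocol 8.2 also cites efficacy information and Phase 3 planning. This stands too: the documents do not support saying that the cardiac comparison alone justifies the arm.

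**General text may cover it.** SAP 6.1 says that descriptive statistics by treatment arm will be given and defines them for continuous variables. So by-arm tables are not excluded. But that text names no variables, and it does not override sections that specify a listing and nothing more.

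**Timing limits what a comparison means.** Scheduled echo follows 14 days off LY2157299 while sorafenib continues, so a visit-wise LVEF contrast of Arm 1 with Arm 3 sets an off-drug reading against an on-drug one. Day 14 vital signs are scheduled predose, so they are trough readings; in extenuating circumstances LY2157299 dosing may also have ended as early as Day 10. This stands, and any summary has to say so.

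**Intervals everywhere would exceed the commitment.** The synopsis promises summaries, plots and listings, not between-arm intervals. Ten measures × five visits (Cycles 2, 3, 4, 6 and Visit 801) × two contrasts would give 100 intervals. This stands, and the request is limited accordingly.

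**Conclusion.** The SAP does not deliver, for ten quantitative echo measures and for blood pressure and heart rate, the by-arm summaries and plots that the protocol synopsis promises for all safety data. The mismatch rests on the text alone and needs no assumption. It matters because the protocol names a safety comparison with sorafenib, with cardiac toxicity an important part, as a purpose of the monotherapy arm. It does not leave that comparison empty, since categorical echo, ECG and adverse-event summaries remain.

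The practical size is only illustrative: about ±3 to ±4 LVEF points for 30 versus 30 at an assumed SD of 6 to 8, widening with attrition. A reader might take this to mean that a drug effect on LVEF can be cleanly estimated. It cannot be read that way, because the SD is assumed, full paired data are assumed, and scheduled echo falls off LY2157299.

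**What to change.** - **SAP 6.12.7.2:** add by-arm descriptive summaries of value and change from baseline, with n at each scheduled visit, for the ten quantitative echo measures. Add the number of patients per arm with post-baseline LVEF below 50%, a limit the protocol already uses in exclusion criterion 18c and Attachment 14. Make the LVEF plot by arm mandatory.
- **SAP 6.12.6:** add the same by-arm summaries for blood pressure and heart rate. Show Day 14 of Cycles 1 and 2 separately, labelled as predose readings within the LY2157299 dosing period.
- **Interpretation note:** state that scheduled Day 1 echo follows 14 days off LY2157299 while sorafenib is continuous.
- **Optional:** between-arm differences with 95% intervals, described as descriptive and best limited to LVEF and blood pressure.

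The cost is a few standard tables and one plot from data already collected. No visit, procedure or patient management changes.

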6.12.7.3. Chest Computed Tomography Scans

Chest computed tomography (CT) scan with contrast of thorax and abdomen for cardiac assessment will be assessed at screening and every 6 months throughout the study and at Visit 801. Alternatively, chest and/or abdomen MRI are allowed.

Chest CT scan with contrast of thorax and abdomen for tumor assessment will be assessed at screening and every 6 weeks starting Cycle 2 Day 14 until radiological disease progression. Alternatively, chest and/or abdomen MRI are allowed.

Results from the CT scan for cardiac assessment and for tumor assessment will be listed separately by treatment, patient and cycle/visit.

6.12.8. Other Data

CT lot numbers of LY2157299 will be listed by treatment, patient and cycle.

6.12.9. Protocol Violations

Significant protocol violations that potentially compromise the data integrity and patients' safety are listed by treatment group for all randomized patients.

Appendix 1 lists the categories of significant protocol violations, the detailed description of each violation within the category, and the method to identify each violation. Further details of study monitoring are in the Study Specific Monitoring Requirements (SSMR) document.

All data collected on the CRF will be checked programmatically for violations. Actual details specifying the programming methods will be given in the ADaM and table, figure, listing (TFL) specifications. Protocol violations that are documented in the monitoring database will be exported to an Excel file for import by statistics. Patients with significant violations may be excluded from the per-protocol population.

6.13. Interim Analyses and Data Monitoring

Three interim analyses are planned. Interim analyses will occur after approximately 10 patients have completed Cycle 1 in the LY2157299 plus sorafenib arm; after approximately 32 patients are randomized and have completed either 3 cycles of treatment, discontinued from study drug, or died; and after approximately 70 deaths have occurred in 3 arms.

Results will be reviewed by an internal assessment committee consisting of the Lilly Medical Director, a Lilly CRP not in contact with study sites, a Lilly statistician, and a PK scientist, if needed. The assessment committee members will review unblinded safety and/or efficacy data at each interim analysis to determine whether there are sufficient safety or futility concerns to

justify the termination of a study treatment arm. Results of the interim analyses will not be communicated to the study sites, unless the interim analyses show evidence of harm.

6.13.1. Interim Analysis #1

The first interim assessment is planned when approximately 10 patients have completed Cycle 1 in the LY2157299 plus sorafenib arm (approximately 3 months from when the first patient is randomly assigned to a treatment arm). It aims to evaluate the PK and safety profiles in the combination arm.

The plan is to continue enrolling patients during the interim assessment unless ongoing safety reviews have raised safety concerns.

6.13.2. Interim Analysis #2

The second interim assessment is planned when approximately 32 patients are randomized and have completed either 3 cycles of treatment, discontinued from study drug, or died (approximately 6 months from when the first patient is randomly assigned to a treatment arm).

The second interim analysis will aim to evaluate that patients treated with LY2157299 monotherapy are not at risk of receiving a treatment that is inferior to sorafenib. Bayesian OS analysis will be carried out at this interim analysis. The LY2157299 monotherapy may be considered futile if the posterior probability of seeing $HR < 0.667$ is $< 10\%$. [Table JBAS.6.7](#) summarizes the likelihood of futility under different HRs. FACTS (version 3.2) was used for simulations.

Table JBAS.6.7. Simulation Results for Interim Analysis #2

n	Allocation	Control Rate Prior	Timing of Analysis	HR	Posterior Probability (HR <0.667) <10%
32	1:2:1	Strong prior for interim analysis #2	First patient visit+7.1 months	1	19%
				1.5	43%
				2	65%
32	1:2:1	Weak prior for interim analysis #2	First patient visit +7.1 months	1	21%
				1.5	40%
				2	61%

Abbreviation: HR = hazard ratio.

6.13.3. Interim Analysis #3

The third interim assessment will be conducted for the purposes of detecting early efficacy signals as well as further evaluating safety observations. This interim analysis will be carried out after approximately 70 deaths have occurred in 3 arms and is projected to take place approximately 17 months after the first patient's visit. Bayesian OS analysis will be carried out at this interim analysis. No formal stopping rules for efficacy will be applied to the interim analyses so that no alpha adjustment will be made. [Table JBAS.6.8](#) summarizes simulation results for type I errors and statistical powers using FACTS (version 3.2).

Table JBAS.6.8. Simulation Results for Interim Analysis 3

N (deaths)	Control Rate Prior	Timing of Analysis	Type I Error	Posterior Probability (HR <1) >0.84
120 (70)	Strong prior for interim analysis #3	first patient visit +20.4 months	14%	74%
120 (70)	Weak prior for interim analysis #3	first patient visit +20.4 months	15%	65%

Abbreviation: HR = hazard ratio.

